**Analytic plan for preliminary clinical outcomes.** We will compare treatment arms using two primary clinical outcomes at immediate post-treatment and one-month follow-up: (1) past 30-day alcohol use frequency/quantity (from *Alcohol Timeline Followback*); and, (2) past 30-day PTSD severity (from *PCL-5*). For **alcohol use**, outcome variables are: % drinking days per week (i.e., days with 1+ drink); % binge drinking days per week (i.e., days with 5+ drinks for men, 4+ for women); and mean number of drinks per week. These variables will be calculated from daily data collected with the *Alcohol Timeline Followback* for 30 days (4 weeks) prior to the last drink before baseline assessment, throughout the 12-week intervention or waitlist period, and throughout the one-month follow up period. Such a weekly measure will allow for estimation of changes per weekly intervention session in the experimental condition as compared to waitlist control.

Our initial unadjusted group comparisons at immediate post-treatment/week 12 and at the end of the one-month follow-up period/week 16 will use a standard t-test (or Wilcoxon non-parametric test, depending on the outcome distribution). Below, we describe models for analyzing adjusted group differences and for analyzing the longitudinal data. We acknowledge that, with the small sample size of this feasibility study, the following models may be optimistic in terms of their capability to reliably estimate and to test interactions. However, they will provide insight into possible effect sizes for planning the larger clinical trial.

We will first compare differences in weekly drinking between the two study conditions at pre-, during, and post- intervention periods using mixed effects models (Model 1):

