## INVESTIGATOR STUDY PLAN - REQUIRED

$Y = b0 + b1*int\_pr + b2*fu\_pr + b3*e + b4*int\_pr*e + b5*fu\_pr*e + \text{other predictors (p\_chars, c\_chars, clinician, study site, etc.)} + \text{random effects}$

Where:  $Y$  = alcohol use dependent variable;  $int\_pr$  = 1 for intervention period, = 0 otherwise;  $fu\_pr$  = 1 for follow-up period, = 0 otherwise;  $e$  = 1 for experimental arm, = 0 for control arm;  $p\_chars$  are participant characteristics (e.g, age, gender);  $c\_chars$  are clinician characteristics (e.g, age, gender); clinician indicators will capture differences in clinician approaches; and, study site indicators will capture differences in location of intervention delivery. Random effects (i.e., participants) will account for unmeasured participant characteristics.

We will examine the linear time trend of intervention effects using interrupted time series analysis (Model 2):

$Y = a0 + a1*wk + a2*int\_pr + a3*wk\_aft + a4*e + a5*wk*e + a6*int\_pr*e + a7*wk\_aft*e + \text{other predictors (p\_chars, c\_chars, clinician, study site, etc.)} + \text{random effects}$

Where:  $Y$  = alcohol use dependent variable;  $wk$  = week number starting with 1 for the first week of data collection;  $int\_pr$  = 1 for intervention period, = 0 otherwise;  $wk\_aft$  = # of week after the intervention starts;  $e$  = 1 for experimental arm, = 0 for control arm; and other predictors and random effects as defined in Model 1. Both models will include multilevel clustering to account for repeated measures from the same participant, as well as correlation among participants receiving intervention in the same study site.

For **PTSD symptoms**, the primary outcome is past 30-day total symptom severity on the *PCL-5*. We will compare study conditions on the *PCL-5* total symptom severity score at each time point using a mixed effects model (Model 3). Fixed effects are: study condition (experimental vs. control), time point (four indicator variables with baseline as the reference group), and interaction of study condition and time point. Similar to Models 1 and 2, we will adjust for participant and clinician characteristics; within-clinician, within-site, and repeated measures correlation; and random effects (i.e., unmeasured participant characteristics).

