**Sample size and power calculation:** Our proposed sample size is based on pilot results and the limited scope of the proposed pilot RCT. A clinically significant effect should be used for planning a future full-scale RCT. For example, a clinically significant change score for the *PCL-5* is 10 points, equal to an effect size of 0.47 using a standard deviation of 21.2. Our projected sample size of 22 completers per study arm will have 80% power to detect a large effect size (0.80) comparing two means using a two independent sample t-test for the unadjusted group comparisons. To detect a smaller effect size (e.g., clinically significant effect size of 0.47), a larger sample size would be needed, but is not feasible due to the scope of the proposed pilot RCT. We used the unadjusted t-test for the power calculations due to the largely unknown assumptions required to calculate the power for a mixed effects model; however, the mixed effects models will have more power than the unadjusted t-test due to the partitioning of the variance among the various components.

**Analytic plan for potential mechanisms of change.** We will examine potential moderators and mediators of intervention effects. We will compare the two treatment arms on these variables at

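### The baseline outcome is not a named covariate in any week-12 or week-16 arm comparison, and the unconditional claim that the mixed models have more power than the t-test is unsupported

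*Combined protocol and SAP*

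**What the plan says.** Section 11 (Study Conditions) places the baseline assessment before randomization, which is done within site and stratified by gender.

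Section 13 (Analytic plan for preliminary clinical outcomes) starts without adjustment: "Our initial unadjusted group comparisons at immediate post-treatment/week 12 and at the end of the one-month follow-up period/week 16 will use a standard t-test", or a Wilcoxon test, depending on the distribution. It continues: "Below, we describe models for analyzing adjusted group differences and for analyzing the longitudinal data".

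- **Model 1 (drinking)** takes the pre-intervention weeks as outcome rows. It has an arm term b3 and arm-by-period terms b4 (intervention) and b5 (follow-up). It has no week-12 term.
- **Model 3 (PCL-5)** has as fixed effects "study condition (experimental vs. control), time point (four indicator variables with baseline as the reference group), and interaction of study condition and time point".
- **Covariates.** The list names participant characteristics (age and gender as examples), clinician characteristics, clinician and site, and is left open. Of the clinician terms it says "clinician indicators will capture differences in clinician approaches". The baseline outcome is not named.

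The sample-size paragraph explains that the t-test was used for power "due to the largely unknown assumptions required to calculate the power for a mixed effects model", and then adds that "the mixed effects models will have more power than the unadjusted t-test due to the partitioning of the variance among the various components". Its PCL-5 benchmark "is 10 points, equal to an effect size of 0.47 using a standard deviation of 21.2".

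**The concern.** In both Model 1 and Model 3 the arm difference at baseline is a free parameter, although randomization makes it zero in expectation. Baseline is therefore used less efficiently than in a contrast that conditions on it. With about 22 completers per arm, precision is scarce, and Section 13 wants these models to inform effect sizes for the larger trial.

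The power sentence tells the reader that the mixed models already secure the gain. Whether they do depends on a correlation that the plan does not give and on a contrast that the sentence does not name.

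A narrower issue is that only the experimental arm has study clinicians (Section 11, Intervention), so clinician indicators can absorb the arm term.

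**Working it through.** **Inputs from the plan.** 22 completers per arm; effect size d = 0.80; SD 21.2; benchmark 10 points; 60 enrolled with 75% retention (Section 25), taken as 30 falling to 22 per arm; four clinicians.

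**Assumed, because not given.** Two-sided 5%; correlation r; equal baseline and follow-up SDs unless stated; normal outcomes; no clustering unless stated.

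**1. The plan's own figure.** The noncentral t with 42 df and noncentrality 0.80/√(2/22) gives 73.6%, not the stated 80%. The normal approximation gives 75.6%, and a one-sided 5% test gives 83.3%. That discrepancy is a separate matter; 73.6% is the reference below.

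**2. Complete data.** Variance relative to the t-test:
- Model 3 arm difference at a visit: 1, so no gain.
- Arm-by-time interaction: 2(1−r).
- Baseline-adjusted (ANCOVA or common baseline mean): 1−r².

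Power at d = 0.80. ANCOVA has five adjusting terms (baseline, gender, three for site), hence 44−2−5 = 37 residual df. The last column also charges for estimating the baseline slope (factor 1+F/38, F on 1 and 38 df).

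| r | t-test | interaction | ANCOVA | ANCOVA, slope estimated |
|---|---|---|---|---|
| 0.2 | 73.6% | 53.6% | 75.1% | 74.0% |
| 0.3 | 73.6% | 59.1% | 77.3% | 76.2% |
| 0.5 | 73.6% | 73.6% | 84.7% | 83.7% |
| 0.7 | 73.6% | 91.7% | 95.1% | 94.6% |

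ANCOVA breaks even with the t-test at r = 0.18. At r = 0 it has 72.2%, a loss of 73.6−72.2 = 1.4 points. At the plan's 10/21.2 = 0.47 and r = 0.5, the first three columns are 33.3%, 33.3% and 42.1%.

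**3. Projected dropout.** Generalized least squares with five visits, compound symmetry and known covariance. Per arm, 3 leave after baseline, 3 after week 4 and 2 after week 8. Variance relative to the t-test on 22 per arm, with power in brackets:

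| r | at visit | interaction | common baseline |
|---|---|---|---|
| 0.2 | 0.983 (74.4%) | 1.423 (58.5%) | 0.953 (75.6%) |
| 0.3 | 0.965 (75.2%) | 1.258 (63.7%) | 0.899 (78.1%) |
| 0.5 | 0.914 (77.4%) | 0.914 (77.4%) | 0.731 (85.8%) |
| 0.7 | 0.850 (80.3%) | 0.557 (93.5%) | 0.491 (95.9%) |

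The interaction breaks even at r = 0.44 to 0.46 over three dropout patterns, and at 0.5 with complete data. If the baseline SD is k times the follow-up SD, the complete-data ratio is 1+k²−2rk, so break-even is r = k/2, or 0.40 at k = 0.8. With dropout, k = 0.8 and r = 0.3, the ratio falls from 1.258 to 1.082.

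**4. PCL-5 points.** The SE of a chance baseline difference is 21.2×√(2/22) = 6.39. The t-test carries r times any such difference: 1.9, 3.2 and 4.5 points per SE at r = 0.3, 0.5 and 0.7. Its 95% half-width is 2.018×6.39 = 12.9 points; for ANCOVA it is 12.5, 11.4 and 9.4.

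**5. Drinking.** With equal weekly correlation ρ and an effect constant over the period, b5 has variance (1−ρ)(1/4+1/4) relative to a single-week t-test: 0.45 at ρ = 0.1 and 0.15 at ρ = 0.7. Here the plan's statement holds. ANCOVA on the 4-week baseline mean has ratio 0.996 to 0.617 for single week 12, and 0.930 to 0.370 for the follow-up mean against a t-test on that mean (ρ = 0.1 to 0.5).

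**6. Clustering.** At an assumed clinician ICC of 0.05 with 22/4 = 5.5 per clinician, t-test, interaction and ANCOVA power fall to 69.1%, 69.1% and 78.5% at r = 0.5. ANCOVA remains the most powerful.

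**7. Clinician indicators.** With waitlist participants coded zero on all four, Model 1 has 10 columns and rank 9. The terms b3, b3+b4 and b3+b5 are not estimable; b4 and b5 are. Adding four post-baseline clinician indicators to a common-baseline Model 3 gives rank 12 of 13, and the week-12 and week-16 effects are not estimable.

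**The case against.** The power claim holds for most contrasts that the plan names. Section 13 says Model 3 will compare the arms at each time point. With all available data used and the projected dropout, that contrast beats the t-test at every r shown, and so do Model 1's period averages. Only the Model 3 interaction at low r falls short, and Section 13 already warns that the models may be optimistic about estimating and testing interactions. All of this stands and limits the point to an unsupported statement.

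A repeated-measures model with baseline as an outcome is a recognised analysis, the t-tests are labelled unadjusted, and the covariate list is open. A reader might infer that baseline is ignored. It is not: it enters through the interaction and the participant random effect, only less efficiently.

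The break-even of 0.45 to 0.5 needs equal SDs. Selecting participants on PCL-5 may narrow the baseline spread, and the plan does not say which time point the SD of 21.2 describes. The threshold could be lower.

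For drinking, percentages are bounded and may hold many zeros, and the baseline window is anchored to the last drink before assessment, so equal correlation is uncertain. A purely linear ANCOVA would lose the plan's distribution check. The fix keeps that check.

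The clinician result depends on the coding, and Model 3 already lists within-clinician correlation. It is secondary. Section 13 also says the full trial should be planned on a clinically significant effect, so this pilot's estimate is not its only basis.

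**Conclusion.** The point holds as a matter of efficiency and wording, of minor to moderate importance in a feasibility pilot. The pre-randomization outcome is not a named covariate in the week-12 and week-16 comparisons, and the power claim rests on no calculation.

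Adjustment is worth about 3 points of power at r = 0.3, 10 to 11 at r = 0.5 and 21 at r = 0.7, against 73.6%. At r near 0.2 it gives little or nothing. These figures rest on an assumed two-sided 5% level, an assumed r, 22 per arm and normal outcomes; normality is least secure for drinking.

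Three stronger readings are tempting and not supported:
- **The claim is false.** It is true for several of the plan's contrasts and can be true for the interaction at higher r.
- **The t-test is biased.** Over repeated trials it is not; it is only less precise, and exposed to chance baseline imbalance in a single trial.
- **The sample size is undermined.** It was set from the t-test and pilot scope, not from this sentence.

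**What to change.** - **PCL-5.** Report the week-12 and week-16 arm differences from Model 3 with a common baseline mean, or from ANCOVA on baseline PCL-5, adjusted for site and gender (the randomization factors).
- **Drinking.** Adjust for the 4-week pre-randomization mean, site and gender. Keep the distribution check, for example with rank-based ANCOVA or robust standard errors if the data are skewed or zero-heavy. Model 1 with a common baseline can supply only the period contrasts.
- **Supportive.** Keep the unadjusted t-test or Wilcoxon test.
- **Clinician.** Keep clinician characteristics and the full set of clinician indicators out of the fixed part of the treatment-effect model. Handle clinician as a random effect in the experimental arm, or in a within-arm analysis.
- **Wording.** Delete the clause on greater power, or make it conditional on the contrast and the baseline correlation. Report the observed correlation for planning the full trial.

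The cost is analysis-plan wording and about 4 to 5 degrees of freedom, with no new data. Site and gender cost about 0.2 to 0.3 points of power; the total loss is at most about 1.4 points if r is near zero.

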## INVESTIGATOR STUDY PLAN - REQUIRED

each time point using mixed effects regression models similar to Model 3, described above. To test for a significant effect of moderators/mediators, we will follow the approach of Kraemer et al., as described below, and will classify baseline factors (e.g., stable patient characteristics, motivation for treatment, perceived provider cultural competency) as moderators and factors that may be related to the intervention as mediators, such as coping skills, self-compassion, and understanding of health information.

In the mixed effects models, we will include the individual mediator (or moderator) as well as the treatment\*mediator (or moderator) interaction term. We will maintain the hierarchy of the interaction and main effect, so that the main effect will stay in the model regardless of its significance if the interaction shows a significant effect. The interpretation of the treatment\*mediator interaction is that the treatment has a differential effect on the outcome through the mediator; for example, participants who understood more of the health information presented during the intervention may have a different response to the treatment than those who understood less. In the case of moderators, the interaction would indicate a differential treatment effect in various subgroups of patients. The interpretation of the model will vary depending on whether the main effects are significant (and which ones) and whether the interaction is significant (with or without significant main effects). Because of the sample size for this pilot RCT, we cannot power the study to identify significant interactions (except for large effects), but can use the interaction effect size to better plan for future efforts.

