## INVESTIGATOR STUDY PLAN - REQUIRED

revising the therapist companion guide. We will then develop a training program for *Signs of Safety* and certify four study clinicians.

We propose to conduct a **two-arm pilot RCT of *Signs of Safety***. We aim to enroll 60 Deaf adults with past-month PTSD and past-month alcohol consumption to participate in 12 weekly individual treatment sessions. The pilot RCT will compare the 12-session protocol of *Seeking Safety + Signs of Safety* toolkit with an assessment-only waitlist control. Across conditions, assessment will occur at baseline, week 4, week 8, immediate post-treatment/week 12, and one-month follow-up/week 16. We will analyze key aspects of feasibility for both study arms (e.g., recruitment, retention, assessment process). Primary clinical outcomes at immediate post-treatment and one-month follow-up are past 30-day alcohol use frequency/quantity and past 30-day PTSD severity. Exploratory analyses will be conducted to examine potential moderators and mediators of change (e.g., motivation for treatment, provider cultural competency, coping skills, self-compassion, understanding of health information) leading to positive outcome. Results from this study will produce feasibility and preliminary efficacy data to support for a full-scale RCT to evaluate *Signs of Safety*, and a community-engaged model for conducting RCTs with Deaf participants.

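### The two-way treatment-by-moderator term averages in pre-randomization outcome rows, so it does not estimate the differential treatment effect the plan reads from it

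*Combined protocol and SAP*

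**What the plan says.** The moderation rule is in Section 13, Analytic plan for potential mechanisms of change. It states: "In the mixed effects models, we will include the individual mediator (or moderator) as well as the treatment"-by-mediator (or moderator) interaction. No moderator-by-time term and no three-way term is named, and no moderation equation is written out. Moderators are fixed at entry: the investigators "will classify baseline factors (e.g., stable patient characteristics, motivation for treatment, perceived provider cultural competency) as moderators". The two-way term is then interpreted: "In the case of moderators, the interaction would indicate a differential treatment effect in various subgroups of patients". The same paragraph concedes that only large interactions could be detected, but says the investigators "can use the interaction effect size to better plan for future efforts".

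The models that receive this term are set out earlier in Section 13. Model 3 (PCL-5) has fixed effects for study condition, "time point (four indicator variables with baseline as the reference group), and interaction of study condition and time point". Models 1 and 2 use weekly drinking, with data collected "for 30 days (4 weeks) prior to the last drink before baseline assessment, throughout the 12-week intervention or waitlist period" and the follow-up month; their period indicators make the pre-intervention weeks the reference. Section 11 (Study Conditions) places randomization after the baseline assessment.

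**The concern.** In all three models the treatment effect sits in the interaction of arm with time or period (b4 and b5 in Model 1; a5 to a7 with their time terms in Model 2; condition by time point in Model 3). In Model 1 the arm coefficient alone, b3, is the pre-treatment gap between arms. A treatment effect that differs by moderator level therefore has to appear as a moderator difference in those arm-by-time terms. A lone arm-by-moderator term has no time component. It pools the moderator-related arm difference over every row, before and after randomization, and the rows before randomization contribute an expected zero.

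The coefficient is thus not the quantity the plan says it is, and under simple conditions it is too small. The plan already accepts that these tests have little power, which leaves the effect size as the main product of the analysis. A diluted effect size passed to the next trial undermines that use.

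**Working it through.** **Plan's own figure.** None is given for moderation. The only power figure in Section 13 is for the unadjusted t-test and does not bear on this point.

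**Inputs from the documents**
- PCL-5 schedule (Section 4): "assessment will occur at baseline, week 4, week 8, immediate post-treatment/week 12, and one-month follow-up/week 16". That is 5 rows per person, 1 of them before randomization.
- Weekly drinking (Section 13): 4 weeks before baseline, 12 weeks of intervention or waiting, about 4 weeks of follow-up. That is about 20 rows, 4 of them before randomization.
- Moderators do not vary over time (Section 13).
- Participant random effects are named. The form of the repeated-measures correlation and the time course of moderation are not given, so both are assumptions below.

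**What the coefficient estimates.** Let g_t be the arm-by-moderator effect at row t. With arm-by-time means fitted and one arm-by-moderator term, generalized least squares estimates the sum of w_t × g_t, where w = S⁻¹1 / (1′S⁻¹1) and S is the within-person covariance. Before randomization g_t has expectation 0.

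**Base case: random intercept, complete data, constant moderation g after randomization.** The weights are equal.
- PCL-5: (0 + g + g + g + g)/5 = 0.80g, a shortfall of 1/5 = 20%.
- Weekly drinking: 16g/20 = 0.80g, a shortfall of 4/20 = 20%.

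**Simulation check** (60 participants, SD 21.2, within-person correlation 0.6, true moderation 10, constant after randomization; theory for the two-way term 8.0). PCL-5 model: the two-way term averaged 8.25 (Monte Carlo standard error 0.19); a moderator-by-arm-by-post-baseline term averaged 10.03. Model 1: 8.44 (0.30) and 9.99.

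**Other assumptions, none of them in the documents**
- AR(1) correlation r, constant moderation. End rows have weight 1 and interior rows 1 − r. PCL-5 shortfall: 1/(2 + 3(1 − r)), which is 1/3.5 = 28.6% at r = 0.5 and 1/2.3 = 43.5% at r = 0.9. Weekly: (1 + 3(1 − r))/(2 + 18(1 − r)), which is 2.5/11 = 22.7% and 1.3/3.8 = 34.2%.
- PCL-5, random intercept with correlation 0.6, 25% lost by week 12 in equal thirds after baseline, week 4 and week 8. A person with k visits carries information k/(1 + 0.6(k − 1)), of which 1/k falls on baseline. Baseline share: [0.0833 × (1 + 0.625 + 0.455) + 0.75 × 0.294] / [0.0833 × (1 + 1.25 + 1.364) + 0.75 × 1.471] = 0.394/1.404 = 28%.
- Linear build-up to week 12, then held, equal weights, measured against the week-12 effect. PCL-5: (0 + 1/3 + 2/3 + 1 + 1)/5 = 0.60, a 40% shortfall. Weekly: (6.5 + 4)/20 = 0.525, a 47.5% shortfall. Measured against the mean effect after randomization (3/4 = 0.75 and 10.5/16 = 0.656), the ratios are 0.60/0.75 = 0.80 and 0.525/0.656 = 0.80. The pre-randomization rows again account for 20%; the rest comes from averaging partial effects during treatment.

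**Precision of the alternatives** (PCL-5, compound symmetry with correlation r, complete data, constant moderation; variance per unit of true effect squared, common factors dropped)
- Two-way term: [(1 + 4r)/5]/0.64. At r = 0.3, 0.44/0.64 = 0.69; at r = 0.6, 0.68/0.64 = 1.06.
- Post-baseline average with baseline as covariate: (1 + 3r)/4 − r². At r = 0.3, 0.475 − 0.09 = 0.385; at r = 0.6, 0.70 − 0.36 = 0.34.
- Week-12 three-way contrast: 2(1 − r). It equals the two-way term when 2(1 − r) = (1 + 4r)/3.2, that is 5.4 = 10.4r, r = 0.52. Below that it is less precise.
- Post-baseline-average three-way contrast: (1 + 3r)/4 + 1 − 2r = 1.25(1 − r). Break-even is at 4(1 − r) = 1 + 4r, r = 0.375.

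**The case against.** The best defence is that the text is shorthand. No moderation equation is written, the plan says it follows a published approach, and it names a differential treatment effect as its target; an analyst could take that to mean a moderator difference in the arm-by-time terms. A three-way term is not ruled out. That much stands. But the two-way term is the only one named, and it is the term the plan interprets, so an analyst who follows the text fits the diluted model.

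The second defence is that little depends on it. The mechanism analyses are labelled exploratory, the limited ability to test interactions is disclosed twice, and the primary arm comparisons and safety monitoring are unaffected. With 60 participants, sampling error may well exceed a 20% shortfall. This limits the weight of the point but does not remove it: an exploratory label excuses imprecision, not estimating a different quantity.

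Three stronger readings are tempting, and the documents do not support them.
- *The estimate is off by up to about half because of the baseline rows.* The 40% and 47.5% figures need an assumed linear build-up and a week-12 yardstick, and the part beyond 20% has another cause.
- *Power is lost as a general matter.* Under constant moderation, the two-way term is more precise than a week-12 three-way contrast when the within-person correlation is below about 0.52. The documents give no correlation.
- *Main effects will be uninterpretable because moderators are uncentred.* The plan does not say how moderators will be scaled, and recoding arm leaves the highest-order interaction test unchanged.

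**Conclusion.** Wrong as written. For a baseline moderator, the stated two-way term in Models 1 to 3 is a weighted average over rows that include pre-randomization data, so it is not the differential treatment effect the plan reads from it. The supportable size is a 20% shortfall against the mean post-randomization moderation, in both the PCL-5 and the weekly drinking models. This rests on a random intercept, complete data and constant moderation after randomization. Serial correlation, dropout or gradual build-up gave larger shortfalls in the cases worked here. They rest on assumptions outside the documents, and against a single visit the shortfall depends on the time course: moderation that peaked early and faded would show a smaller one at week 12. The consequence is confined to the exploratory moderator estimates. It deserves correction because those estimates are intended for planning and the repair is cheap.

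**What to change.** In Section 13, Analytic plan for potential mechanisms of change, write out the moderation model and its estimand. Either of two forms will do:

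1. Arm by moderator in post-baseline data only, with the baseline outcome as covariate, averaged over post-baseline visits and also reported by visit.
2. Moderator by arm by time point in Model 3, and moderator by arm by period (Model 1) or by the period and slope terms (Model 2), with all lower-order terms including moderator by time.

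Under either form, report the post-baseline average and the week-12 and week-16 contrasts with confidence intervals, and state which of them is the effect size carried into planning.

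The cost is a few lines of text and slightly longer models; no new data, visits or participants are needed. There are two trade-offs. A three-way contrast can be less precise than the present term when the within-person correlation is low (below about 0.52 for a single visit, and below 0.375 for the post-baseline average, under constant moderation). Under the compound-symmetry conditions worked above, the first form averaged over visits avoids this. On the other hand, the first form leaves out participants with no post-baseline outcome, whereas the second keeps their baseline row; the plan should say how that sits with its intent-to-treat statement.
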